1.0 Objectives / Specific Aims

- Primary: To determine the safety and efficacy of a single SinuSonic intervention.
- Secondary: Secondary objectives of this study is to determine:
 - the safety and efficacy of a twice daily SinuSonic intervention over 2 weeks.
 - the safety and efficacy of a twice daily SinuSonic intervention over 4 to 6 weeks.

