number of antibiotics have been approved for the treatment of acute sinusitis; however, there is no conclusive evidence that oral antibiotics, topical antibiotics, or topical antifungal agents are effective in the treatment of chronic sinusitis, and their use remains controversial, particularly due to concerns over emerging resistance (Ebbens 2006; Fokkens 2007; Videler 2008). As chronic sinusitis is characteristically an inflammatory disease, the anti-inflammatory effects of corticosteroids could be expected to be of benefit. There are no clinical studies published on the use of systemic corticosteroids for the treatment of chronic sinusitis without polyps, although there is evidence that systemic corticosteroids are effective at reducing the size of nasal polyps and improving rhinitis symptoms (Fokkens 2007; Van Zele 2010). Medical treatment with nasal corticosteroids (as currently available for treatment of rhinitis) is considered a first step in the treatment of chronic sinusitis; however, the data on sprays or drops does not suggest they are very effective.

Patients with chronic sinusitis currently have limited medical options for treatment and no medication is approved for the treatment of chronic sinusitis. Standard nasal spray pumps suffer from a number of drawbacks and they are considered suboptimal for reliable drug delivery to target sites beyond the nasal valve (Aggarwal 2004). Current congestion medications are not always fully effective. This study aims to test the safety and efficacy of the SinuSonic device on adults with moderate to severe nasal congestion. SinuSonic is a medical device that utilizes sound and pressure combined with normal breathing to relieve nasal congestion. The study will take place over the course of 4 to 6 weeks starting with a baseline assessment. This study will use patient responses to measure how effective SinuSonic devices are in treating adults with moderate to severe congestion in adults.

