3.0 Intervention to be studied

- Initial intervention: Subjects will use the SinuSonic device for 3 minutes in the clinic setting.
- Secondary intervention: Subjects will use SinuSonic device twice daily for 3 minutes in the home setting for 14 days.
- Tertiary intervention: Subjects will continue to use the SinuSonic device twice daily for 3 minutes in the home setting for 2-4 weeks.

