4.0 Inclusion and Exclusion Criteria/ Study Population

The study population will consist of individuals present for care at the Otolaryngology clinics at the Medical University of South Carolina with nasal congestion, friends/family members of patients presenting for care at MUSC’s Otolaryngology clinics.

Inclusion Criteria

- Adults \geq 18 years of age
- Complaints of nasal congestion present for 2 weeks or more and a qualifying nasal congestion score of >5 (10 point VAS scale).

Exclusion Criteria

- Fixed structural cause of nasal congestion (moderate or severe septal deviation, moderate or severe nasal valve collapse, Grade 3-4 polyp)
- Inability to read and understand English
- Allergic sensitivity to silicone or any other component of device
- History of severe nose bleeding within last 3 months
- Anticoagulation (Aspirin ok)
- Known pregnancy
- Current nasal crusting or ulceration revealed on rhinoscopy
- Inability to perform treatment due to underlying medical condition

- Topical decongestant use in last week

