9.0 Study Design / Methods

This study is designed as a pilot study.

Data will be collected by the ENT fellows as well as the subjects themselves throughout the entirety of the study. The data will consist of answers from subjects for questionnaires asked by the clinicians as well as self-reported answers from the subjects.

Safety will be monitored throughout the study based on monitoring of adverse events, performing nasal, measuring vital signs (i.e. blood pressure, pulse) and weight, and through collection of concomitant medication information.

The period of observation for collection of non-serious adverse events extends from the time the subject gives informed consent until completion of the End-of-study visit or Early Termination Visit. Serious adverse events (SAE) will be reported from the time of informed consent through 30 days after the last use of the SinuSonic. Adverse event data listings will be reviewed by SinuSonic at regular intervals throughout the study. In addition, SinuSonic will be alerted of Adverse Events of interest via automated emails programmed in the EDC system.

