9.1 Schedule of Events

Phase	Screening	Treatment		
		0	2	4-6
Week	0	0	2	4-6
Visit	1	2	3	4
Informed Consent	x			
Inclusion/Exclusion Criteria	x			
Medical History	x			
Height	x			
Rhinoscopy	x		x	
Vital Signs	x			
Pregnancy Test	x			
Distribution of SinuSonic	x			
NOSE Questionnaire	x		x	x
SNOT-22	x		x	x
TNSS Questionnaire	x		x	x
Global Assessment of Nasal/Sinus Problems	x	x	x	x
PNIF	x	x	x	

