10.0 Data Management

All analyses and graphs will be performed with SPSS 24.0, Sample Power 3.0, and Sigma Plot 10.0 (SPSS, Chicago, IL.). Disease information and demographic variables, such as age, gender, race, quality of life (QOL) scores, and VAS scores will be summarized using frequencies, means, and standard deviation as appropriate. Outcome metrics will be compared between baseline and 5 minutes (AIM 1), baseline and 2 weeks (AIM 2), and baseline and 4-6 weeks (AIM 3). Categorical variables will be compared using Chi Square or McNemar's test. Continuous variables will be compared using One-Way ANOVA with repeated measures followed by post-hoc analysis. Data regarding safety and patient satisfaction will be summarized for each time point. A p-value ≤ 0.05 will be considered statistically significant. Due to the exploratory nature of this study, no p-value correction (ie Bonferroni) will be applied. If appropriate, subgroup analysis can be performed based on underlying disease classification (allergic rhinitis, nonallergic rhinitis, CRSsNP, CRSwNP).

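### The Aim 1 VAS change compares a rating of the past week with a rating of the moment after use, so it cannot be read as change over a single use

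*Combined protocol and SAP*

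**What the plan says.** Section 1.0 gives the primary objective as "To determine the safety and efficacy of a single SinuSonic intervention". The two secondary objectives use the same safety-and-efficacy wording for 2 weeks and for 4 to 6 weeks of home use. Section 2.0 adds: "This study will use patient responses to measure how effective SinuSonic devices are".

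Section 3.0 describes the single use: "Subjects will use the SinuSonic device for 3 minutes in the clinic setting". Every subject receives the device; no sham, control group or randomisation is described. Section 9.0 states: "This study is designed as a pilot study".

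Section 9.1 repeats two measures at Visit 2, the "Global Assessment of Nasal/Sinus Problems" and PNIF. I take the first to be the block of five VAS lines on the questionnaires, which ends in an overall assessment line.

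Section 10.0 sets the comparison, "Outcome metrics will be compared between baseline and 5 minutes (AIM 1", with matching baseline comparisons for Aims 2 and 3, and the criterion: "A p-value ≤ 0.05 will be considered statistically significant". It calls the study exploratory when explaining why p-values are not corrected.

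**The concern.** A before-after difference is interpretable only if the same question is asked both times. At baseline the subject averages over a week. Five minutes after use the same subject reports the present moment. Congestion on arrival at the clinic may be better or worse than the week's average, and any such gap enters the Aim 1 VAS change as if it had happened during the use.

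Aim 1 is the primary aim, the VAS is one of only two measures scheduled at Visit 2, and Section 2.0 says effectiveness is to be measured by patient responses. A pre-use current rating cannot be recovered once a subject has used the device, so no later analysis can repair the omission.

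A second, lesser matter is the wording of the aims. They speak of efficacy, while every test compares subjects with their own baseline.

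**Working it through.** **Step 1. The VAS forms side by side.**

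| Form | When | Period asked about |
|---|---|---|
| Attachment 1 (one line, congestion) | Before use | Last two weeks |
| Attachment 2 (five lines) | Baseline, before use | Last week |
| Attachment 4 (five lines) | 5 minutes | Now, after use |
| Attachment 5 (five lines) | 2 weeks | Last week |
| Attachment 7 (five lines) | 5 weeks | Last week |

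No form asks about the current state before use. The 2-week and 5-week forms match Attachment 2, so the VAS comparisons for Aims 2 and 3 are like with like.

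**Step 2. What the Aim 1 VAS change contains.** Let W be the past-week rating (Attachment 2), C the current rating just before use (not collected) and Y the rating after use (Attachment 4). Then

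Y − W = (Y − C) + (C − W).

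The first bracket is the change over the single use. The second is purely a change of time frame. Only W and Y are observed, so the data cannot divide the sum between the brackets. C − W may have either sign: a negative mean inflates apparent improvement, and a positive mean hides real improvement.

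**Step 3. Other Aim 1 measures.** PNIF is scheduled at Visits 1 and 2 and has no recall period. Attachment 4 also carries four improvement ratings scored 0 to 3. These ask about change directly and need no baseline. Neither measure has the mismatch. The ratings run from none to high, so they cannot record worsening.

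**Step 4. How small a shift matters (illustration).** The plan gives N = 40 but no SD, effect size or power, so there is no figure of its own to reproduce. Assumptions: SD of VAS change 1.5, 2.0 or 2.5 points; a two-sided paired t-test at 0.05 standing in for the post-hoc comparison; 40 analysed, or 32 after an assumed 20% loss (40 × 0.8).

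Smallest significant mean change = t(0.975, n − 1) × SD / √n.

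- n = 40, t = 2.023: 2.023 × 1.5 / 6.325 = 0.48; for SD 2.0, 0.64; for SD 2.5, 0.80.
- n = 32, t = 2.040: 2.040 × 1.5 / 5.657 = 0.54; for SD 2.0, 0.72; for SD 2.5, 0.90.

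Probability that a pure time-frame shift δ towards improvement is significant with no effect of use = 1 − F(t(0.975, n − 1)), where F is the noncentral t distribution with n − 1 degrees of freedom and noncentrality δ√n / SD. With no shift it is 2.5% in that direction.

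| n | Assumed δ | SD 1.5 | SD 2.0 | SD 2.5 |
|---|---|---|---|---|
| 40 | 0.25 | 18% | 12% | 9% |
| 40 | 0.5 | 54% | 34% | 23% |
| 40 | 0.75 | 87% | 64% | 46% |
| 40 | 1.0 | 98% | 87% | 69% |
| 32 | 1.0 | 95% | 78% | 59% |

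These are general properties of a before-after test of this size. They show how small a shift would be enough, not how large it is in this study.

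**The case against.** The strongest reply is that Aim 1 does not depend on the VAS. No primary endpoint is named, and PNIF and the improvement ratings both escape the mismatch. That stands, and it confines the defect to one of three Aim 1 efficacy measures. It does not cure it: Section 10.0 still calls for baseline against 5 minutes on the outcome metrics, and the VAS is one of the two measures scheduled for that comparison. All three measures also remain open to placebo response.

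A second reply is that every SD and shift in the illustration is assumed. That is so, and the conclusion does not rest on them; it rests on the wording of the forms.

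Three stronger readings are tempting but not supported.

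- *A reader might infer that the single-arm design is itself an error.* The study is declared a pilot with exploratory analysis, for which one arm is a legitimate choice. Section 10.0 defines statistical significance; it does not say that significance proves the device caused the change. What remains is the wording of the aims and a limit on the conclusion.
- *A reader might infer that the mismatch favours the device.* The documents give no basis for its direction.
- *A reader might infer material regression to the mean from the entry rule,* "a qualifying nasal congestion score of >5 (10 point VAS scale". The plan does not say which form supplies that score and gives no SD or reliability, so no size can be assigned. Nor could the rule alone confine the effect to the later aims, because the congestion line is also on the 5-minute form.

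**Conclusion.** The point holds for the Aim 1 VAS and should be fixed. As written, its change from baseline combines change over the single use with a change of time frame, of unknown size and direction, and the two cannot be separated afterwards. This follows from the attachments as supplied and assumes that no other pre-use VAS is collected.

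The VAS for Aims 2 and 3, PNIF and the improvement ratings are not affected. The wording of the aims is secondary: with every subject on the device and every test against baseline, p ≤ 0.05 shows that scores moved, not that the device moved them.

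**What to change.** **Main change.** Immediately before first use, have each subject complete the five VAS lines of Attachment 4 under a stem asking how troublesome each symptom is *right now*. In Section 10.0, name these as the Aim 1 VAS baseline, and report PNIF change and the improvement ratings beside the VAS change. Keep Attachment 2 as the VAS baseline for Aims 2 and 3. Since the baselines then differ, analyse the Aim 1 VAS as its own paired comparison, not as one level of an ANOVA across all visits.

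**Secondary change.** In Section 1.0, word all three aims as assessing safety and estimating within-subject change from baseline. In Section 10.0, report changes with 95% confidence intervals and state that p ≤ 0.05 against baseline is not evidence that the device caused the change.

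**Cost.** One five-line form at an existing visit, plus wording in Sections 1.0 and 10.0; no extra subjects or visits. Subjects may remember their pre-use mark minutes later, and the conclusion becomes more modest. The new form removes the time-frame mismatch but not placebo response.

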2.0 Background

Chronic sinusitis/rhinosinusitis with or without nasal polyps is a multifactorial disease associated with asthma, cystic fibrosis, primary ciliary dyskinesia, acetylsalicylic acid intolerance, and possibly allergy. It is defined as an inflammation of 1 or more paranasal sinuses and is considered chronic when it lasts longer than 8 weeks (Slavin 2005). It is almost always accompanied by concurrent airway inflammation and in many cases is preceded by rhinitis symptoms.

Chronic sinusitis is one of the most commonly diagnosed diseases in the United States. It has been estimated to affect approximately 20 million Americans (Benson 1998) and up to an estimated 16% of the adult population annually in Europe (Huvenne 2009). There are currently no approved medications for treatment of chronic sinusitis. The cardinal clinical signs and symptoms of chronic sinusitis include nasal blockage/congestion, facial pain or pressure, mucosal erythema and thickening, purulent nasal secretions, headache, and a reduction in smell (Fokkens 2007). Chronic disease is distinguished in part by persistence of characteristic symptoms for ≥ 8 weeks (Slavin 2005).

Patients with nasal polyps tend to have a more pronounced nasal obstruction and loss of smell while those without nasal polyps tend to report headache and post-nasal drip more frequently. However, the pattern of symptoms mostly overlaps between patients with and without nasal polyps.

Current Treatment Options: There is clear need for a better medical therapy that reduces chronic sinusitis symptoms, thus improving morbidity and quality of life and decreasing the need for surgery. Currently, there are no approved medications for the treatment of chronic sinusitis. A

number of antibiotics have been approved for the treatment of acute sinusitis; however, there is no conclusive evidence that oral antibiotics, topical antibiotics, or topical antifungal agents are effective in the treatment of chronic sinusitis, and their use remains controversial, particularly due to concerns over emerging resistance (Ebbens 2006; Fokkens 2007; Videler 2008). As chronic sinusitis is characteristically an inflammatory disease, the anti-inflammatory effects of corticosteroids could be expected to be of benefit. There are no clinical studies published on the use of systemic corticosteroids for the treatment of chronic sinusitis without polyps, although there is evidence that systemic corticosteroids are effective at reducing the size of nasal polyps and improving rhinitis symptoms (Fokkens 2007; Van Zele 2010). Medical treatment with nasal corticosteroids (as currently available for treatment of rhinitis) is considered a first step in the treatment of chronic sinusitis; however, the data on sprays or drops does not suggest they are very effective.

Patients with chronic sinusitis currently have limited medical options for treatment and no medication is approved for the treatment of chronic sinusitis. Standard nasal spray pumps suffer from a number of drawbacks and they are considered suboptimal for reliable drug delivery to target sites beyond the nasal valve (Aggarwal 2004). Current congestion medications are not always fully effective. This study aims to test the safety and efficacy of the SinuSonic device on adults with moderate to severe nasal congestion. SinuSonic is a medical device that utilizes sound and pressure combined with normal breathing to relieve nasal congestion. The study will take place over the course of 4 to 6 weeks starting with a baseline assessment. This study will use patient responses to measure how effective SinuSonic devices are in treating adults with moderate to severe congestion in adults.

3.0 Intervention to be studied

- Initial intervention: Subjects will use the SinuSonic device for 3 minutes in the clinic setting.
- Secondary intervention: Subjects will use SinuSonic device twice daily for 3 minutes in the home setting for 14 days.
- Tertiary intervention: Subjects will continue to use the SinuSonic device twice daily for 3 minutes in the home setting for 2-4 weeks.

3.1 Device Instructions

Instructions for use:

1. Hold the SinuSonic device at a 45-degree angle
2. Deep breathe
3. Hold the SinuSonic to your mouth and blow out into the mask of the SinuSonic. The goal here is to hear the “target flutter” sound that is desired during treatment with the SinuSonic
4. Put the device over the nose using the nasal mask
5. Breathe in and out thru the nose if possible. If nasal breathing is not possible it is ok to open mouth to breathe in and try and hear the “target flutter” sound when you breathe out
6. You will feel a little resistance to breathe out and a vibration sensation from a speaker in the device
7. Remove the device to “blow the nose” if nasal drainage occurs
8. Return the device to the nose then breathe in and out thru the nose to try and hear the “target flutter” sound
9. Time of use is 2-5 minutes of nasal breathing with the device - as tolerated

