Attachment 2: Baseline Questionnaires**BASELINE QUESTIONNAIRES**

PATIENT QUESTIONS													
How long have you had nasal problems?	<3 months 3-6 months 6-12 months 1-3 years >3 years												
OVER THE LAST WEEK, HOW TROUBLESONE HAVE THE FOLLOWING SYMPTOMS BEEN? PLEASE PLACE A MARK ON THE LINE.													
	
  
 Not troublesome	Worst thinkable/troublesome	
   
 ◆————◆	◆————◆	
  
	Not troublesome	Worst thinkable/troublesome	◆————◆	◆————◆	◆————◆	◆————◆	◆————◆	◆————◆	◆————◆	◆————◆	◆————◆	◆————◆
Not troublesome	Worst thinkable/troublesome												
◆————◆	◆————◆												
◆————◆	◆————◆												
◆————◆	◆————◆												
◆————◆	◆————◆												
◆————◆	◆————◆												
Nasal blockage/obstruction/congestion	◆————◆												
Nasal discharge/drainage out of the front or back of nose	◆————◆												
Pain/pressure in nose or sinuses	◆————◆												
Sense of smell	◆————◆												
OVERALL ASSESSMENT OF NASAL AND SINUS PROBLEMS	◆————◆												

BASELINE Total Nasal Symptom Score

Please answer all questions to the best of your ability. This information will assist us in understanding and treating symptoms. Please rate how your symptoms have been over the **past week**.

Symptom	None	Mild: Symptom clearly present but easily tolerated	Moderate: Symptom bothersome but tolerable	Severe: Symptom difficult to tolerate – interferes with activities
Nasal congestion/obstruction	0	1	2	3
Runny nose/secretions	0	1	2	3
Nasal itching	0	1	2	3
Sneezing	0	1	2	3
Sleep difficulty with nasal symptoms	0	1	2	3

BASELINE NOSE scale

Please help us to better understand the impact of nasal obstruction on your quality of life by completing the following survey. Thank you!

Over the past **ONE month**, how much of a problem were the following conditions for you?

	Not a problem	Very mild problem	Moderate problem	Fairly bad problem	Severe problem
Nasal congestion or stuffiness	0	1	2	3	4
Nasal blockage or obstruction	0	1	2	3	4
Trouble breathing through my nose	0	1	2	3	4
Trouble sleeping	0	1	2	3	4
Unable to get enough air through my nose during exercise or exertion	0	1	2	3	4

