Attachment 4: Follow Up Questionnaire**FOLLOW UP 5 MINUTES**

AFTER USING SINUSONIC, HOW TROUBLESOME ARE THE FOLLOWING SYMPTOMS? PLEASE PLACE A MARK ON THE LINE.		
	Not troublesome	Worst thinkable/troublesome
Nasal blockage/obstruction/congestion		
Nasal discharge/drainage out of the front or back of nose		
Pain/pressure in nose or sinuses		
Sense of smell		
OVERALL ASSESSMENT OF NASAL AND SINUS PROBLEMS		

[figure not shown]
[figure not shown]
Change in nasal symptoms and use of device

Please rate changes in your nasal symptoms and use of device.

Symptom	None	Mild	Moderate	High
Improvement in nasal obstruction/stuffiness	0	1	2	3
Improvement in nasal drainage/discharge	0	1	2	3
Improvement in nasal or sinus pressure	0	1	2	3
Improvement in ability to smell	0	1	2	3
Pain with use of device	None	Mild	Moderate	Severe
Comfort and ease of use	Poor	Low	Moderate	High
Bleeding:	Yes	No		

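### Nose-blowing is allowed during the in-clinic session but not standardised before the baseline PNIF, so the Aim 1 PNIF change can include simple nose clearing

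*Combined protocol and SAP*

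**What the plan says.** - **Objective.** Section 1.0 gives the primary objective as "To determine the safety and efficacy of a single SinuSonic intervention". Section 3.0 describes that intervention: "Subjects will use the SinuSonic device for 3 minutes in the clinic setting".
- **Nose-blowing.** Section 3.1, step 7: "Remove the device to “blow the nose” if nasal drainage occurs". Step 8 then continues the session: "Return the device to the nose then breathe in and out thru the nose". Blowing is thus conditional on drainage, and part of the instructions for use.
- **Analysis.** Section 10.0: "Outcome metrics will be compared between baseline and 5 minutes (AIM 1"). The comparison is within subject, and the plan has no comparator arm. Section 10.0 contains no adjustment or sensitivity analysis for nose-blowing.
- **Timing.** The schedule in Section 9.1 lists PNIF at Visit 1 (week 0), Visit 2 (week 0) and Visit 3 (week 2). PNIF appears only as a schedule row. Preparation of the nose, number of efforts and choice of value are not described.
- **Ratings.** The baseline VAS (Attachment 2) asks "OVER THE LAST WEEK, HOW TROUBLESONE HAVE THE FOLLOWING SYMPTOMS BEEN". The 5-minute VAS (Attachment 4) asks "AFTER USING SINUSONIC, HOW TROUBLESOME ARE THE FOLLOWING SYMPTOMS".
- **Recording.** The readable text of Attachment 4 covers symptoms, pain, comfort and bleeding. It has no item on whether the nose was blown.

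**The concern.** A before-after comparison is interpretable only if the two measurements are taken under the same conditions, apart from the intervention. Under the plan as written, a subject with secretions may give a baseline PNIF with an uncleared nose, blow the nose during the session, and then give the second PNIF with a cleared nose. Part of the rise would then be what any nose blow achieves.

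PNIF is the only airflow measurement on the schedule, and so the Aim 1 outcome least exposed to expectation effects. If clearing contributes to it, the most credible evidence for a single session is weakened. If nobody records who blew, the contribution cannot be examined afterwards.

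**Working it through.** **The plan's own figure.** There is none to reproduce. Section 5.0 states 40 subjects without a power calculation, an effect size or a PNIF standard deviation.

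**Which PNIF values serve Aim 1.** Section 10.0 compares baseline with 5 minutes, and Section 9.1 has two week-0 PNIF measurements. The second is not labelled as the 5-minute one, but no other PNIF on the schedule can fill that role.

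**Bias in the mean.** Let *f* be the share of subjects who blow during the session and *c* the mean PNIF gain from clearing in those who do. With an inert device, the expected mean change is *f × c*. Neither is in the documents. I assume that clearing raises flow (*c* > 0).

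**How much is enough for significance.** From the documents: n = 40 (Section 5.0) and p ≤ 0.05 (Section 10.0). Assumed: a two-sided test, and a paired t-test standing in for the post-hoc contrast after repeated-measures ANOVA. The critical value is t(39) = 2.023, so the mean change that just reaches significance is 2.023/√40 = 0.32 SD of the paired change.

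**Illustration 1: mean shift over all 40 subjects.** Assumed SD of change: 25 or 35 L/min. Noncentrality = (shift/SD) × √40.

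| Mean shift, L/min | SD, L/min | Noncentrality | Chance of p ≤ 0.05, inert device |
|---|---|---|---|
| 5 | 25 | 0.20 × 6.32 = 1.26 | 23% |
| 5 | 35 | 0.143 × 6.32 = 0.90 | 14% |
| 10 | 25 | 0.40 × 6.32 = 2.53 | 69% |
| 10 | 35 | 0.286 × 6.32 = 1.81 | 42% |

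These shifts are averages over blowers and non-blowers. Since *c* = shift/*f*, a mean shift of 5 L/min needs 5/0.25 = 20 L/min per blower if a quarter blow, or 5/0.5 = 10 if half do. A mean shift of 10 needs 40 or 20.

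**Illustration 2: only a share blows.** Simulation with an inert device, 40 subjects, and a gain of *s* SDs of the paired change in a random share *f*. Chance of p ≤ 0.05, against a nominal 5%:

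| Share who blow | s = 0.25 | s = 0.5 | s = 1.0 |
|---|---|---|---|
| 25% | 7% | 12% | 29% |
| 50% | 12% | 32% | 79% |
| 100% | 34% | 87% | about 100% |

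The result runs from near nominal to almost certain, depending on two quantities that the documents do not give.

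**The VAS, side by side.** The baseline form asks about the past week and the 5-minute form about the state after use. A nose blow just before the baseline form would not change what a one-week recall rating measures, so clearing cannot put the two ratings on the same footing.

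**The case against.** **Nose-blowing belongs to the intervention.** Steps 7 and 8 are instructions for use, so the effect of a session used as directed includes clearing what drains. This has force as a choice of what to estimate. It does not count against a cleared baseline: secretions loosened during use are blown out after that baseline and still count for the device. Only what a plain blow would have removed beforehand drops out.

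**Silence is not conduct.** A reader might infer that PNIF will in fact be measured uncleared before and cleared after. The documents do not support that. They give no PNIF procedure, and clinic staff may already have subjects clear the nose. What stands is that preparation is unspecified and the plan permits the imbalance. Likewise, one cannot say flatly that no form records nose-blowing, because two figures in Attachment 4 are not shown.

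**The fix is not a control.** A subject who drains would still have blown more often before the second PNIF than before the first, and there is no arm that only blows the nose. This stands, and it limits what may be claimed for the fix.

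**Proportion.** This is an exploratory 40-subject pilot with no named primary endpoint. Section 2.0 says that effectiveness will be measured by patient responses, and eligibility requires congestion rather than drainage. This stands as a reason to treat the size as open. It is no reason to leave a cheap correction undone when the primary objective includes efficacy and is tested at p ≤ 0.05.

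**Conclusion.** The point holds for PNIF. The plan permits nose-blowing between the two week-0 PNIF measurements and does not standardise the nose before the first, so in subjects who drain the Aim 1 change can include simple clearing, in the direction of benefit. This rests on two inferences: that the second week-0 PNIF is the 5-minute one, and that clearing raises flow.

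The size is unknown. The percentages above show only that a modest mean shift could matter at n = 40; they are not estimates of the false-positive risk in this trial. A reader might take the 42% to 69% range as the expected inflation. The documents do not support that, because it needs an average gain of 10 L/min over all subjects, including those who never blow.

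A reader might also infer that clearing the nose first would repair the blockage and discharge VAS lines. It would not, because the baseline and 5-minute forms ask about different periods. That is a separate defect with its own remedy.

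**What to change.** 1. In Sections 3.1 and 9.1, state that every subject blows the nose in the same standard way before each PNIF: Visit 1 baseline, Visit 2 after use, and week 2. Week 2 is included because a cleared baseline needs a matching later measurement.
2. Add a yes/no item to the 5-minute form (Attachment 4): nose blown during the session. This shows how many subjects are affected and lets their PNIF changes be described separately.
3. For the VAS, add a current-state rating immediately before use, with the same time frame as the 5-minute form.

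Items 1 and 2 cost one instruction line and one tick-box, with no extra visit or equipment. Item 3 adds one short form. The before-after PNIF difference may become smaller. The report should still say that a single-arm comparison, even with standard clearing, does not separate the device from all non-device effects.
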